³ During the study 12-lead ECG's should be conducted prior to blood collection.

⁴ Dosing should occur within 8 days after site received MRI validation from the vendor, infusion duration 1hr +/- 10 mns.

⁵ Two sequencial MRIs will be carried out at this visit.

Corporate Confidential Information

⁷ PK Blood for MCS110: All post-dose samples to be taken after end of infusion. The "1 hr" time point should be taken immediately after the end of infusion.

⁶ These samples are not required to be taken fasting.

⁹ SAE reporting from time of signing informed consent until 30 days after subject has stopped study participation.

¹⁰ AEs to be reported from time of first study drug administration on Day 1 until study completion.

¹¹ Alcohol and drug screen, pregnancy test, hematology and clinical chemistry : screening results can be used at baseline if baseline is planned in the next 7 days following screening.

Corporate Confidential Information

¹⁵ Hematology and clinical chemistry for safety purpose will be analyzed locally before any dosing day. Any other visits saftey samples will be analyzed by the central lab

¹⁶ At week 12, after dosing, patient's treamtment will be unblinded.

If Day 1 treatment is placebo, Assessment Schedule B1 will be applied from the next visit.

If Day 1 treatment is MCS110 Assessment Schedule B2 will be applied from the next visit Corporate Confidential Information

¹⁸ For Part B1 patients, an unscheduled visit 8 should be planned 4 weeks after visit 8 (week 20) as administration day of dose 5.

For Part B2 patients, an unscheduled visit 7 should be planned 4 weeks after visit 7 (week 16) as administration day of dose 5.

¹⁹ Collection of these samples is discontinued as of 30-Aug-2016

²⁰ Visit 109 (Part B1) will not be performed if patients had visits optional dosing visits 116 and 117 (schedule B1)

²¹ Visit 208 (Part B2) will not be performed if patients had visits optional dosing visits 215 and 216 (schedule B2). Corporate Confidential Information

Assessment Schedule (Part B – re-dosing)

	RLP	redosing Screening									R	(edo	sin	g Tr	eatr	men	t											Redo	sing Fo	ollow-up visit	EoS
Visit Numbers	1	2		3	1	4	Τ		5			6	6			7	7				8		Γ		9			10	11	12 (optional) ¹³	777
Visit Numbers for Crned Programming ¹	301	302		30	3	304	4	3	05			30	-			30				-	08				309			310	311	312 (optional) ¹³	780
Weeks	-	-		1		2			4				3			1					16				20			24	36	48	60
Months									1			2	2				3				4		Γ		5			6	9	12	15

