3.2 Part B and C

3.2.1 Study Design Part B

The study CMCS110X2201 Part B is a randomized, double-blind, placebo-controlled, parallelarm, exploratory PoC clinical trial with 2:1 randomization of MCS110 to placebo for the first dose followed by open-label multiple doses. Part B first dose will be administered double-blind, placebo-controlled. All patients will receive active treatment after the first dose and the study will continue as an open label study.

Day 1 blinding will be maintained until week 12, which corresponds to the fourth dose for the potential Day 1 MCS110 patients. After patient reaches week 12 (Visit 7), Day 1 treatment received by the patient will be un-blinded in order to allow Day 1 placebo patients to receive a fourth dose of MCS110.

If patient received placebo at Day 1, then, the patient will follow Assessment Schedule Part B1 after Visit 7.

If patient received MCS110 at Day 1, then, the patient will follow Assessment Schedule Part B2 after Visit 7.

In the multiple dose Part B patients receive up to 4 doses of 10 mg/kg MCS110 administered once every 4 weeks. Two additional MCS110 doses will be administered, if MCS110 is well tolerated and if a reduction in tumor volume of >50% can be demonstrated after the 3^{rd} MCS110 dose by MRI taken before the 4^{th} dose.

Confidential

The primary outcome of Part B of the study will be tumor volume after multiple doses of MCS110 monitored by MRI. The primary outcome will be assessed 8 weeks after the last dose of MCS110, a time point, where free drug is expected to decline rapidly, based on modeling and simulations of free MCS110 concentrations.

Patients who meet the eligibility criteria at screening will be admitted to baseline evaluations. All baseline safety evaluation results must be available prior to dosing. Safety assessments will include physical examinations, ECGs, vital signs, standard clinical laboratory evaluations (hematology, blood chemistry, urinalysis) adverse event and serious adverse event monitoring. This study will be carried out primarily in the out-patient setting.

In order to monitor the duration of the tumor size reducing effect of MCS110, patients will have follow-up visits every 3 months for up to 2 years to document changes in growth of the residual tumor or to detect recurring tumor by MRI. The time intervals of 3 months are according to the standard of care for patients, who had undergone surgery.

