If after 6 patients have completed the 4 week treatment, the PoC criterion is not reached, the probability to reach PoC with the addition of 6 new patients will be assessed, and if this probability is less than 10% the trial may be stopped for futility.

For illustration, an example of a trial path simulation with skeptical and neutral priors on mean treatment effect in MCS110 group is shown below (Figure 9-1):

Figure 9-1 Example of a sample path

The left plot displays the skeptical analysis and the right plot the neutral analysis.

The blue dots represent the posterior mean in the MCS group and the black dots represent the posterior means in the placebo group as more patients contribute data.

The green dots show the probability of MCS110 being superior to placebo, and the pink dot the probability to be better by 40%.

In this example, the PoC criterion is reached after 3 patients when neutral prior (second graph) is used, and after 4 patients when skeptical prior (first graph) is used.

Part B:

Tumor volumes will be listed and descriptively summarized at each MRI assessment time by treatment groups (treatment group 1 = MCS110 throughout the trial, treatment group 2 = Placebo for the first dose and MCS110 from the second dose) accordingly. Moreover, the number and percentage of patients with complete tumor response will be presented, and the time that the complete tumor response is observed will be listed by patient and treatment group.

In addition, we may pool treatment groups by matching the 1st dose of MCS110 in treatment group 1 to the 2nd dose (1st of MCS110) in treatment group 2. More specifically, for treatment group 2, the measurement right before patients receiving the first dose of MCS110 (2nd dose from screening) will be treated as the new baseline and assessment time-points will be adjusted accordingly. This may apply to all analyses in Section 9 if necessary.

Part C:

Tumor volumes will be listed and descriptively summarized at each MRI assessment time by treatment arm (treatment arm 1 = MCS110 3 mg/kg, treatment arm 2 = MCS110 5 mg/kg, treatment arm 3 = MCS110 10 mg/kg) accordingly. Moreover, the number and percentage of patients with complete tumor response (CR) will be presented, and the time that the complete

tumor response is observed will be listed by patient and treatment arm. In addition, incidences of patients with partial response (PR), stable disease (SD) and progressive disease (PD) will be listed by treatment arm.

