The same model as above will also be applied to compare the efficacy of the 3 mg/kg and 5 mg/kg to the 10 mg/kg dose (instead of Placebo).

Part B and C (referenced as Part B* hereafter)

Part B includes all data from multiple dosing Parts. In Part B, treatment group 1 = MCS110 throughout the trial, treatment group 2 = Placebo for the first dose and MCS110 from the second dose. In Part C, treatment arm 1 = MCS110 3 mg/kg, treatment arm 2 = MCS110 5 mg/kg, treatment arm 3 = MCS110 10 mg/kg, for patients in treatment arms 1 and 2 that switch to 10 mg/kg after 3 doses, they will be included in their original treatment group for the first 3 doses and will added in a separate group after that (4= MCS110 3 mg/kg for 3 doses and 10 mg/kg afterwards and 5= MCS110 5 mg/kg for 3 doses and 10 mg/kg afterwards), no re-calculation of baseline will occur for the people who change treatments.

Tumor volumes will be listed at each MRI assessment timepoint till the end of the study by treatment groups.

Part B*: MCS110 data only, by including data starting from the 1st dose of MCS110 in all treatment groups of Parts B and C. More specifically, for Part B treatment group 2, the measurement right before patients receiving the first dose of MCS110 (2nd dose from screening) will be treated as the new baseline and assessment time-points will be adjusted accordingly. Summary statistics of the consolidated tumor volume for the raw values, percent change and absolute change from baseline.

Arithmetic mean (+/-) SE on percent change from baseline vs time plot will be produced for Part B*. Waterfall plot of the maximum reduction until 8 Weeks after last dose will be produced in regards of number of doses received.

Overall Time to complete tumor ablation will be summarised up to the primary endpoint (8 weeks after the last MCS110 dose), along with a summary of overall time to $\geq 50\%$, and $\geq 80\%$ ablation. The number and frequency of patients reaching each level will also be included in the summary.

Overall Time to complete ablation is the time (in weeks) - from first MCS110 dose to the first time when there is no tumor detected. Overall time to $\geq 50\%$, and $\geq 80\%$ ablation is the time from first MCS110 dose to reach maximum ablation of [50%, 80%) and [80%, complete) respectively.

Part C

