Additional time-profiles will be provided graphically for circulating monocytes, Creatine Kinase and ALT, AST (liver enzymes). This will be presented for Part A*, Part B* and Part C.

Special clinical laboratory evaluations

All laboratory data will be listed by treatment, patient, and visit/time and if ranges are available abnormalities will be flagged. Summary statistics will be provided by treatment and visit/time.

Adverse events

All information obtained on adverse events will be displayed by treatment and patient. The number and percentage of subjects with adverse events will be tabulated by body system and preferred term with a breakdown by treatment. An adverse event starting in one period and continuing into the next period is counted only in the onset period. A subject with multiple adverse events within a body system [within a treatment period] is only counted once towards the total of this body system.

Frequency counts will be produced for adverse events by maximum severity and the same table produced for adverse events that are related to study drug. An overall summary of the number of adverse events categorised by serious, related, leading to discontinuation and death. Summary statistics will be produced for the duration of adverse events by preferred term.

Additional listing of adverse events of special interest will also be provided. Adverse Events of special interest will be identified by medical review of the preferred terms occurring in the data in addition to periorbital edema already identified.

In Part C all summary tables will also be provided by age group (<18 years and ≥18 years).

Concomitant medications / Significant non-drug therapies

All concomitant therapies will be listed by treatment group and patient.

10 Reference list

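### Counted from first MCS110, Part B week-16 scans come only from patients extended to dose 5, so the raw week-16 mean tumour change is not comparable with weeks 12 and 20

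*SAP*

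**What the plan says.** **The display.** SAP 7.1 asks for the following: "Arithmetic mean (+/-) SE on percent change from baseline vs time plot will be produced for Part B". The population is Part B*, meaning MCS110 data from all treatment groups of Parts B and C. Summary statistics of raw values, percent change and absolute change go with it. Patients given placebo first are re-baselined at their first MCS110 dose and their time points are shifted. SAP 7.1.1 leaves missing data missing. Protocol 9.4.2 also requires, for Part B itself: "Tumor volumes will be listed and descriptively summarized at each MRI assessment time by treatment groups".

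**The visits.** In the Protocol's Assessment Schedules, B2 is MCS110 first and B1 is placebo first. (SAP 2.3 swaps these labels; the Protocol's are used here.) The schedule footnotes say:
- B2: "For Part B2 patients, an unscheduled visit 7 should be planned 4 weeks after visit 7 (week 16) as administration day of dose 5".
- B1: "For Part B1 patients, an unscheduled visit 8 should be planned 4 weeks after visit 8 (week 20) as administration day of dose 5".
- Week 20 in B2: "Visit 208 (Part B2) will not be performed if patients had visits optional dosing visits 215 and 216 (schedule B2"). So week 20 is covered by visit 208 or by dosing visit 216.

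**The condition for doses 5 and 6.** Protocol 3.2.1: "Two additional MCS110 doses will be administered, if MCS110 is well tolerated and if a reduction in tumor volume of >50% can be demonstrated" on the scan after the third MCS110 dose. Protocol 5.5.5.2 repeats the response threshold. It adds that there must have been no treatment-related safety issue that delayed dosing, and that the tumour must not already have been eliminated.

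**The concern.** A mean-versus-time plot invites the reader to follow one group of patients along the curve. Here the Part B group shrinks at week 16 to those who had done well enough at week 12 to be extended, and is complete again at week 20. A reader judging whether dose 5 adds shrinkage, or whether tumours regrow after it, could be looking at a change in who was scanned. The SAP has no rule for the optional visits in this plot: no common patient set, no n per time point, no split by extension. Its own description of Part B (2.3) stops at four doses and does not mention the extension.

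**Working it through.** **1. Visits on the SAP's clock (weeks from first MCS110).**

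| Week | B2 (MCS110 first) | B1 (placebo first; study week minus 4) | Who is scanned |
|---|---|---|---|
| 12 | visit 7 | visit 8, study week 16 | all |
| 16 | visit 215 (7 UNS1) | UNS1, study week 20 | extended to dose 5 only |
| 20 | visit 208 or 216 | visit 109 or 117, study week 24 | all |

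The Part B week-16 subset is defined by the week-12 value of the plotted variable.

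**2. Inputs for the size.** The plan gives no figure for this effect, so there is none to reproduce.
- Patients: 11 in Part B, 18 in Part C (Protocol 1.1, study experience to date).
- Average Part B reduction after three doses: about 50% (Protocol 1.4). Assumption: the median volume ratio at week 12 is 0.5, exactly at the threshold, so about half of patients qualify.
- SD s of the log ratio: 0.28 to 0.42, from 0.2 × √2 and 0.3 × √2 (Protocol 9.13). Using it as the spread at week 12 is an assumption.
- Share of that variance that persists from week 12 to week 16, r: 0.5 or 1. The √2 combines a baseline and a follow-up error of equal size, and weeks 12 and 16 share the baseline scan, so r = 0.5 needs no true difference between patients. r = 1 treats all of it as lasting.
- No true change after week 12 and no eliminated tumours.

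**3. Formulas.** With log ratio ~ N(log 0.5, s):
- all patients: mean ratio = 0.5 × exp(s²/2)
- qualifiers (week-12 ratio below 0.5), at week 16: mean ratio = 2 × 0.5 × exp(s²/2) × Φ(−r·s)

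| s | r | Φ(−r·s) | All patients | Qualifiers | Shift, Part B alone |
|---|---|---|---|---|---|
| 0.28 | 0.5 | 0.444 | −48.0% | −53.8% | −5.8 points |
| 0.28 | 1 | 0.390 | −48.0% | −59.5% | −11.5 points |
| 0.42 | 0.5 | 0.417 | −45.4% | −54.5% | −9.1 points |
| 0.42 | 1 | 0.337 | −45.4% | −63.2% | −17.8 points |

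**4. Pooled Part B\* curve.** If all 18 Part C patients are scanned at week 16 with the same mean, Part B supplies 5.5 of 23.5 patients, a weight of 5.5/23.5 = 0.234. The shift is 0.234 × 5.8 = 1.4 to 0.234 × 17.8 = 4.2 points. The SE of that pooled mean, on the same assumptions, is about 3 to 5 points.

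**5. A second set of assumptions.** A simulation took percent change as normal with mean −50% and SD 10 to 25 points (assumed), fully persistent. The dip is 8 to 20 points for Part B alone and 2 to 5 points pooled with Part C at the same mean.

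**6. What can reverse it.**
- *Eliminated tumours.* Take week-12 changes of −15, −25, −35, −45, −52, −54, −56, −60, −100, −100, −100. The week-12 mean is −642/11 = −58.4%. Only −52, −54, −56 and −60 qualify, so the week-16 mean is −222/4 = −55.5%. The curve rises although nothing changed.
- *Part C response.* In the step-5 simulation with 0 to 30% of tumours eliminated (assumed), a Part C mean of −35% gives anything from a 2-point dip to a 6-point rise. With none eliminated, a Part C mean of −65% gives a dip of 4 to 7 points.

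**The case against.** Several points against the concern are sound.

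- **The quoted curve is not a Part B curve.** It pools Part C, whose week 16 is a regular treatment visit. The artefact there is 1 to 4 points, at most about one SE. This stands for the plot. It does not cover the Part B summaries by treatment group in Protocol 9.4.2, where Part C does not dilute: group 1 at week 16 and group 2 at study week 20 contain only extended patients.
- **The upper size stretches its source.** The SD in Protocol 9.13 is residual within-subject error, under identical treatment effects in all patients. Treating all of it as lasting is an upper bound; 6 to 9 points fits that definition better.
- **A model-based time course already exists.** SAP 7.1.2 fits a repeated-measures ANCOVA to Part B*, with estimates by visit and a plot. If fitted by likelihood with an adequate covariance structure, it can allow for a gap that depends on the observed week-12 value. The weakness is confined to the raw means.
- **No decision hangs on week 16.** The Part B primary outcome is tumour volume 8 weeks after the last dose.

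Three stronger readings are tempting and not supported:
- *The curve must dip.* Protocol 5.5.5.2 also removes eliminated tumours, the best responses, and Part C may differ, so the direction is not guaranteed.
- *No unextended Part B patient has a week-16 scan.* On the study-week clock, every placebo-first patient has a routine one; the statement holds only from first MCS110.
- *Week-16 laboratory profiles look cleaner for the same reason.* Protocol 5.5.5.2 does not count an isolated CK rise as a safety concern, SAP 8 does not say its time-profiles are means, and the documents give no basis for a size.

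**Conclusion.** The concern holds in a limited form. Counted from first MCS110, the Part B week-16 value rests on a response-selected subset, and the raw mean there is not comparable with weeks 12 and 20. That follows from the schedules, the extension conditions and the re-basing rule, without any assumption about the data.

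The size does rest on assumptions: median reduction at the 50% threshold, SD 0.28 to 0.42, no true change after week 12, and few eliminated tumours. A spurious dip is then expected of about 6 to 9 points for Part B alone with half the variance persistent, up to about 18 with all of it, and about 1 to 4 points in the pooled Part B* curve. The documents give no between-patient SD and no elimination rate.

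The pooled figure also assumes that all Part C patients are scanned at week 16. The Part C schedule marks an MRI there, but the text of its footnote is not in the supplied copy, and patients in the 10 mg/kg arm may stop after four doses. Six doses in Part B also depended on approval of version 04, so extension did not turn on response alone; that makes the subset smaller, not more representative. The primary endpoint is untouched.

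**What to change.** In SAP 7.1, for Part B* and for the Part B by-visit summaries:

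1. Compute all-patient raw means and plots only at visits scheduled for every Part B patient (weeks 4, 8, 12, 20 and the later follow-up visits, counted from first MCS110).
2. Print n at each time point.
3. Show values from the optional dose-5 visit (visit 215; UNS1 of B1) in a separate curve or row for extended patients, beside the four-dose patients.
4. Make the repeated-measures ANCOVA of SAP 7.1.2 the main time-course display. One check first: it works on the log ratio, which does not exist for an eliminated tumour, and SAP 7.1 gives its square-root alternative only with the single-dose analysis. Say what applies here.

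If the same patients contribute at weeks 12, 16 and 20, the artefact is zero in the set-up above. The cost is SAP wording and one extra grouping in the plot program, with no change to data collection or treatment. The downside is that there is no all-patient raw Part B mean at week 16.

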Protocol synopsis

Title of study: A Phase II randomized, double-blind (Part A, B and C), placebo controlled (Part A and B only) study to assess safety, tolerability and efficacy of MCS110 on tumor size in patients with pigmented villonodular synovitis (PVNS).

Confidential

Purpose and rationale:

Part A

This study is designed as a PoC (proof of concept) study of MCS110 in PVNS. The purpose of the present study is to measure the clinical response to MCS110 treatment in PVNS patients within 4 weeks after a single intravenous (i.v.) dose of 10 mg/kg of MCS110 using magnetic resonance imaging (MRI) to assess tumor volume, and to assess safety and tolerability in this patient population.

The study will also provide information on pharmacokinetic (PK) and pharmacodynamic (PD) effects of MCS110, including the assessment of hematological changes and measurement of biomarker responses of bone turnover. Corporate Confidential Information

The ultimate goal will be to assess whether treatment of PVNS with MCS110 can replace surgery, either in the primary or relapse setting. Thus, a multi-dose study Part B in PVNS is planned if the study Part A demonstrates PoC for M-CSF blockade in PVNS.

Part B

A single dose treatment with MCS110 has shown efficacy with an average reduction in tumor volume of 40% (29-50%). In order to better understand the longer-term tolerability and efficacy of MCS110, a multiple dose part is conducted (Part B). The ultimate goal of this portion of the study will now be to assess whether treatment of PVNS or GCTTS with multiple doses of MCS110 can lead to a complete tumor ablation and thus replace surgery, either in the primary or relapse setting.

Part C

With the aims/goals to achieve maximum tumor volume reduction and tumor cell eradication and be as safe as possible it appears most appropriate to explore the efficacy and safety of MCS110 at doses lower than 10 mg/kg. In Part C of the study it will be tested whether repeated administration of doses lower than 10 mg/kg MCS110 may have the same efficacy as multiple doses of 10 mg/kg of MCS110 while simultaneously showing improved AE profile. In addition to tumor volume reduction efficacy will be assessed by reduction of metabolic activity Corporate Confidential and on the tumor tissue level Corporate Confidential Information

Objectives:

Primary objectives:

Part A

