9.13 Sample size calculation

Part A

The trial will be analyzed after each patient has completed Day 28 visit and the tumor volume has been assessed by MRI. The trial may stop at any time if the PoC criterion (see Section 9.4.2) is met, and therefore no fixed sample size is planned. However, a maximum of 12 evaluable patients will be recruited, with a 2:1 ratio MCS110 to placebo. The minimum number of patients to declare PoC is 3, i.e., 2 MCS110 patients and one placebo patient.

Imatinib is known to inhibit the macrophage colony-stimulation factor receptor (CSF-1R). In a recent report it has been demonstrated, that imatinib treatment led to a partial response within 2 months of treatment and a complete response after 5 month of treatment in one case of advanced recurrent PVNS (Blay et al 2008). Given, that imatinib is not a particularly strong inhibitor of CSF-1R (Dewar et al 2005), treatment with an Ab against M-CSF, such as MCS110, which specifically blocks CSF1 signalling is expected to show a 40% reduction in one month.

From scan-rescan MRI reproducibility experiments (Ng et al 2010), it is expected to observe up to 10% variability in measurement of tumor size due to imaging techniques, parameters used, types of tumor (e.g., size or shape) or observers. Due to inter-occasional variability, and due to a potential inflation of variability in the presence of treatment, the actual within-subject variability may be bigger, i.e., the within subject variability in the MCS110 treated patients is assumed to be about twice as much, i.e., 20%. For the placebo patients both 10% and 20% variability assumptions are considered. As a very conservative scenario, we assume also a 30% variability in both groups.

This leads to 3 possible scenarios:

- Scenario 1: 10% within subject variability for the placebo patients and 20% for the MCS110 patients.
- Scenario 2: 20% within subject variability for the placebo and MCS110 patients
- Scenario 3: 30% within subject variability for the placebo and MCS110 patients

Assuming the treatment/placebo effects to be identical in all patients, the residual error of the log ratio relative to baseline is then approximately 0.1 * sqrt(2) or 0.2 * sqrt(2) or 0.3 * sqrt(2), depending on group/scenario.

Novartis	Confidential	Page 136
Amended Protocol Version v07 (Clean)		Protocol No. CMCS110X2201

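### SAP 7.1 names time to ≥50% and ≥80% ablation but defines both by mutually exclusive bands of maximum ablation, so the counts can be understated and the timing rule is ambiguous (minor, descriptive)

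*SAP*

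**What the plan says.** SAP 7.1, in the Part B* text, plans to summarise time to complete ablation up to 8 weeks after the last MCS110 dose, together with time to ≥50% and time to ≥80% ablation. It adds: "The number and frequency of patients reaching each level will also be included in the summary".

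The definitions follow. Complete ablation is timed "from first MCS110 dose to the first time when there is no tumor detected". The two partial levels are defined differently: each "is the time from first MCS110 dose to reach maximum ablation of [50%, 80%) and [80%, complete) respectively".

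Two other outputs in the same section bear on the point:
- "Waterfall plot of the maximum reduction until 8 Weeks after last dose will be produced in regards of number of doses received"
- "Tumor volumes will be listed at each MRI assessment timepoint till the end of the study by treatment groups"

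Protocol 9.4.2 does not plan the partial levels. For Part B it plans the number and percentage of complete responders, and "the time that the complete tumor response is observed will be listed by patient and treatment group". Neither document gives another definition of time to ≥50% or ≥80%.

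**The concern.** The names of the two partial levels are cumulative: a tumor that has shrunk by 85% has also reached 50%. The definition is not cumulative. Its half-open intervals, tied to the levels by the word respectively, put each patient in at most one band and put complete responders in neither. A count built this way does not give the number reaching each level.

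The clock is also unclear. Complete ablation uses first occurrence, while the partial levels refer to reaching maximum ablation. That may mean the scan at which the maximum occurs, or the scan at which the patient first enters the band. Two programmers could follow the text faithfully and produce different tables.

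What is at stake is how a small multiple-dose data set is described: how many patients get close to tumor elimination, and how fast. With 29 patients, moving one or two changes a percentage by 1/29 = 3 to 2/29 = 7 points.

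**Working it through.** The plan gives no figure for this summary, so there is none to reproduce. The check compares the name with the definition and then asks how large the difference could be.

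**1. Set comparison.** Let M be a patient's maximum reduction.

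| Level | What the name includes | What the bands include | Left out on a literal reading |
|---|---|---|---|
| ≥50% | [50%, 80%), [80%, complete), complete | [50%, 80%) | M ≥ 80%, including complete |
| ≥80% | [80%, complete), complete | [80%, complete) | complete |

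Name and definition agree only if nobody falls in a higher category.

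**2. Invented example (illustration only).** Percent reduction at weeks 4, 8, 12, 16, 20, 28:
- P1: 30, 45, 55, 60, 62, 60
- P2: 40, 55, 70, 82, 85, 83
- P3: 50, 75, 90, 100, 100, 100
- P4: 10, 20, 30, 35, 40, 38
- P5: 52, 60, 65, 70, 72, 78

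Cumulative counts at ≥50%, ≥80% and complete are 4, 2 and 1. The literal bands give 2, 1 and 1. For the two patients in the [50%, 80%) band (P1 and P5), the first crossing of 50% is at weeks 12 and 4 (median 8), while the maximum is at weeks 20 and 28 (median 24). If the text means first entry into a band, P2 and P3 also pass through both bands. The counts are then 4 and 2, and there is no delay.

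**3. Possible size of the count loss, literal reading.** Inputs:
- 29 patients: 11 in Part B plus 18 in Part C (Protocol section 1, under Study CMCS110X2201).
- Median best reduction R = 50%, borrowed from the average after three 10 mg/kg doses (Protocol 1.4).
- Log SD s of 0.3, 0.424 and 0.6, which is an assumption. The middle value is 0.3 × √2 from Protocol 9.13, but that is a within-subject error derived by "Assuming the treatment/placebo effects to be identical in all patients". It is not a between-patient spread, which the documents do not give.

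Formula: patients lost from ≥50% = 29 × Φ((log 0.2 − log(1 − R))/s). For R = 0.50 the numerator is log 0.4 = −0.916.

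| R | s = 0.3 | s = 0.424 | s = 0.6 |
|---|---|---|---|
| 50% | 29 × 0.001 = 0.0 | 29 × 0.015 = 0.4 | 29 × 0.063 = 1.8 |
| 45% | – | 29 × 0.0085 = 0.2 | 29 × 0.046 = 1.3 |
| 60% | – | 29 × 0.051 = 1.5 | 29 × 0.124 = 3.6 |

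A log-normal model never yields complete response, so the loss of complete responders from the ≥80% count is not quantified here.

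**4. Possible size of the timing gap.** I simulated patients whose maximum lies in [50%, 80%) and took time to maximum minus first crossing of 50%. The median path assumes 40% reduction at week 4 (Protocol synopsis, single dose) and 50% at week 12, linear on the log scale between and flat after. Patient SD was 0.3 to 0.6 on the log scale.
- No scan noise: mean gap 5.2 to 6.3 weeks. The path forces this, because every maximum falls at week 12. With the plateau starting at week 8 the gap is 2.2 to 2.9 weeks; at week 4 it is 0.
- Scan log SD 0.1 to 0.2: 5.2 to 8.4 weeks if the last MRI is at week 20, 7.1 to 10.1 at week 24, and 7.8 to 11.0 at week 28. Much of this is chance choice of the lowest scan on a flat stretch.
- First-entry reading: gap zero. On the week-12 path, 0 to 4.2% of all simulated patients jump over the [50%, 80%) band between scans, which is up to about 7% of those reaching ≥50%.

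The path ignores the planned week-12 dose change for some Part C patients, so these figures are illustrative only.

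**The case against.** The best defence is that the bands are deliberate. The intervals [50%, 80%), [80%, complete) and complete split all patients with at least 50% reduction into best-response categories, in keeping with the waterfall plot of maximum reduction planned just before. That is a legitimate display, and complete responders are not lost, because they have their own summary in the same paragraph. On this view only the name is at fault. This stands as far as it goes, and it is why relabelling is an acceptable fix. It does not make the bands report the number reaching each level.

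The consequence is also small. The summary is descriptive. Disjoint counts can be added up, the waterfall plot shows the maxima, and first-crossing times can be derived from the volume listing. SAP 1.2 allows minor changes by a note to file. All of this stands.

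A reader might infer three stronger things that the documents do not support:
- **That a published table will carry mislabelled rows.** The SAP text available is prose; no table layout is visible.
- **That response times are biased late by a known number of weeks.** The delay arises on only one of two readings, and its size follows from an assumed response path.
- **That efficacy conclusions or dosing are affected.** The week-12 dose rule and the arm extension in Protocol 3.2.2 and 5.5.5.2 rest on their own volume-reduction thresholds and do not use this summary.

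**Conclusion.** The concern holds as a minor inconsistency in SAP 7.1. The mismatch between the cumulative names and the disjoint bands is explicit in the text, and nothing elsewhere resolves it. On the literal reading the number reaching each level is understated whenever a patient reaches a higher category. The timing rule is an ambiguity to be settled, not a demonstrated bias.

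The size cannot be determined from the documents. At a 50% median and log SD 0.3 to 0.6, about 0 to 2 of 29 patients are lost from the ≥50% count; a higher median would lose more. The timing gap is zero to several weeks, depending on the reading, the response path and scan noise. These figures assume log-normal best reductions and apply a 10 mg/kg average to a group that includes patients started on 3 and 5 mg/kg.

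**What to change.** Either of two changes to SAP 7.1 is enough:
- **Make the definition match the name.** Define time to ≥50% (≥80%) ablation as weeks from first MCS110 dose to the first MRI, up to 8 weeks after the last dose, at which the consolidated volume reduction is at or above the threshold. Count cumulatively, so that patients who go on to ≥80% or complete ablation stay in the lower levels.
- **Make the name match the definition.** Keep the bands, label them as best-response categories (50% to <80%, 80% to <complete, complete), and report time to maximum reduction.

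The cost is a sentence or two of SAP wording and a small derivation change. No new data are needed.
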